4.8 Mothers' Procedures

• A questionnaire will be administered at enrolment from which information regarding their sociodemographics, sexual behaviour and reproductive health issues including obstetrical records will be obtained. Antiretroviral use and regimen will be recorded for all the HIV+ mothers. Assessment of nutritional status/BMI will be done using standard anthropometric indices. A physical examination will be done at every visit by the study clinician. Mothers will be enrolled at 28-36 weeks gestation and followed up at delivery, 10 days and 6, 10, 14, 24, 36, 48, 72 and 96 weeks postpartum thus totaling 11 visits during the study period. Data can still be collected in cases of missed visits provided the participant turns up within the seven day window period of the scheduled visits. The participant may be asked to discontinue if she consecutively fails to turn up for at least two successive scheduled study visits without any reason(s).

Biological specimens blood, cord blood, amniotic fluid, breast milk urine and stool will be collected at different visit with the respective quantities and purposes as shown in the **Table** 1 below.

	Total Volume of Specimen Required						
Visit	HIV Status	Blood* (mL)	Stool** (grams)	Breast Milk* (mL)	Urine *** (mL)	Amniotic Fluid (mL)	Cord Blood (mL)
1	HIV+	30	20	-	100	50	
In Pregnancy	HIV-	25	20		100	50	
2 Delivery	HIV+	10	20		100	50	50
	HIV-	5	20		100	50	50
3 7 -10 days pp	HIV+	-	If delivery visit is	10	100		
	HIV-	-	missed some of the samples are collected.	10	100		
4 6 Weeks/1½Months pp	HIV+	20	20	10	100		
	HIV-	10	20	10	100	50	
5 10 Weeks /2½ Months	HIV+	20	20	10	100		
рр	HIV-	10	20	10	100		
6 14 Weeks, 3½Months	HIV+	20	20	10	100		
рр	HIV-	10	20	10	100		
7 24 Weeks/6 Months pp	HIV+	20	20	10	100		
	HIV-	10	20	10	100		
8 36 Weeks/9 Months pp	HIV+	20	20	10	100		
	HIV-	10	20	10	100		
9 48 Weeks/1 year	HIV+	20	20	10	100		
pp	HIV-	10	20	10	100		
10 72 Weeks /1 ^{1/2} years	HIV+	20	20	10	100		
	HIV-	10	20	10	100		
11 96 Weeks/2 years	HIV+	20	20	10	100		
	HIV-	10	20	10	100		

Table 1: Types and total Volumes of Maternal Specimen Required

*Generally blood samples, amniotic fluid cord blood and breast milk will be tested for trend in immune profiles and coinfections.

Stool samples will be tested for intestinal parasites * Urine

urinalysis

Procedure	Specimen	1	2	3	4	5	6	7	8	9	10	11

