4.10.18 Sample Size Determination

Pocock's formula was used to determine sample size (n) required:

- $n = \frac{p_1(1-p_1)+p_2(1-p_2)(Z_{\alpha}-Z_{\beta})^2}{(p_1-p_2)^2}$
- Where p_1 and p_2 are proportion of success in population 1 and 2
- Z_{α} and Z_{β} are values of standard normal distribution
- α = Significance level
- $\beta = Power$

3% incidence rate has been assumed to factor in for the a high risk of vertical transmission in the breastfeeding period for the few anticipated acute HIV infection²³⁴.With the advent of cell phones the % loss to follow up may not be that bad and cannot be similar for the first and second year. Factored in the worst case scenario of a 15% and 20% loss to follow-up during the first and second year respectively, a minimum sample size required computed using **STATA** is 1200 (600 HIV+ and 600 HIV-) mothers. Assuming a 15% and 20% loss to follow up in the first and second year of the study respectively, should leave us with at least the 417 infants. The sample size has power to predict diseases outcomes of HEU children which must culminate in their improved management. The sample size has not factored in sample sizes of sub-studies linked to it in the **Appendices' Section 6.2**. Should there be sub-studies, they should fit within this parent protocol. These aim to address all the research gaps highlight throughout the literature review.

	a) HIV Chronic Infection		b) HIV Acute Infection	c) HIV Negative	Outcomes
Comorbidities	Treatment experienced Immune	Treatment naive Profiles for dif	ferent comorbidities c	ombinations	Prevalence and incidence of comorbidities, comorbidities trends relating comorbidities to
HBV HCV CMV					immunological profiles, pregnancy outcomes, vertical transmission of infections, patterns and
Anaemia Diabetes Nutritional Status					transmission linkages, infant/child growth and neurodevelopment
Hypertensive disorders					

Table 5: Pictorial Depiction of the Stratification

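### Section 4.8 makes data collection conditional on a seven-day window and lets the study discontinue women after two unexplained missed visits, so obtainable outcome data are forgone

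*Protocol*

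**What the plan says.** Protocol section 4.8 (Mothers' Procedures) has mothers "followed up at delivery, 10 days and 6, 10, 14, 24, 36, 48, 72 and 96 weeks postpartum thus totaling 11 visits during the study"; enrolment is the first of the eleven. On late attendance it says: "Data can still be collected in cases of missed visits provided the participant turns up within the seven day window period of the scheduled visits". It does not say whether the window runs before, after or on both sides of the scheduled date. On repeated absence it says: "The participant may be asked to discontinue if she consecutively fails to turn up for at least two successive scheduled study visits", and the sentence then limits this to absence without a reason.

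The only recovery provision found is in Table 1, where part of the sampling from a missed delivery visit may be done at 7 to 10 days.

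Three other places bear on this. Section 4.3 follows mother and infant as a pair for two years. Section 3.1 lists among its objectives the incidence of maternal coinfections over 24 months, postpartum HIV incidence, and infant growth, morbidity and mortality. Section 4.10.18 treats loss only as a reduction in numbers: "Factored in the worst case scenario of a 15% and 20% loss to follow-up during the first and second year respectively".

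**The concern.** Nothing in this design is protected by refusing late data or by asking a woman to leave. There is no treatment to stop and no per-protocol exposure to preserve. The window sentence is worded as a condition for collecting data, not as a scheduling target. The discontinuation rule can turn two missed visits into permanent loss of the pair. No section provides for infant vital status or other outcomes after a late attendance or a discontinuation.

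Two things are at stake. The first is information: some outcomes are measured so rarely that a single refused visit removes them. The second is bias. The protocol's own background (section 1.11) links delayed antenatal care, non-disclosure and social disadvantage to poor maternal and infant outcomes. Weak engagement with study visits could plausibly go with the same circumstances. An analysis plan can model missing data but cannot restore specimens and outcomes that the protocol declines to collect.

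**Working it through.** The plan gives no figure for the effect of these rules, so there is none to reproduce. The inputs are the visit schedule and wording in section 4.8, the assay timing in Table 2 and section 4.10.5, and the planned loss in section 4.10.18.

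**1. Share of each gap covered by the window.** The share is 7 or 14 days divided by the gap in days.
- 10 to 14 weeks: 28 days; 7/28 = 25%, 14/28 = 50%.
- 24 to 36 and 36 to 48 weeks: 84 days each; 7/84 = 8%, 14/84 = 17%.
- 48 to 72 and 72 to 96 weeks: 168 days each; 7/168 = 4%, 14/168 = 8%.

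The window is therefore least generous where visits are furthest apart. This is a share of calendar time, not of data lost.

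**2. Follow-up exposed to discontinuation.** A woman who misses weeks 14 and 24 and is then discontinued loses weeks 36, 48, 72 and 96: four visits and 96 − 24 = 72 weeks, 72/96 = 75%. The effect shrinks later. Missing weeks 48 and 72 forfeits one visit (24/96 = 25%), and missing weeks 72 and 96 forfeits none.

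**3. Outcomes that depend on a late visit.** Section 4.10.5 and Table 2 screen mothers for HBV, HCV and CMV only at enrolment and at the 24-month visit. A woman discontinued earlier, or seen eight days late at the last visit with the window strictly applied, contributes nothing to the incidence of these infections. HIV testing of negative women is scheduled at every visit (Table 2), so each refused visit also widens the interval in which a seroconversion can be dated.

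**4. Illustration of how often two successive misses occur.** Assume each of the 10 post-enrolment visits is missed independently with probability p. Let a be the probability of no run of two so far with the last visit attended, and b the same with the last visit missed. Then a' = (a + b)(1 − p), b' = a·p, and P(run) = 1 − a − b after 10 visits.
- p = 5%: 2%, about 13 of 600 women
- p = 10%: 8%, about 48
- p = 15%: 17%, about 101
- p = 20%: 27%, about 164

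Under that assumption these are ceilings for the rule, which needs absence without a reason and is discretionary. The protocol gives no miss rate.

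**5. Illustration of what outcome-related loss would do.** Planned retention is 0.85 × 0.80 = 68%. If all 32% lost are unobserved and their risk is R times that of the retained, observed risk divided by true risk is 1/(0.68 + 0.32R). For R = 1, 1.5, 2 and 3, risk is understated by 0%, 14%, 24% and 39%. This concerns all planned loss. The part due to these two rules is unknown, and R is an assumption.

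**The case against.** The strongest reply is that the discontinuation rule is narrow. It applies only to absence without a reason, so a woman who reports illness or hardship is outside it. It says she may be asked, not that she is removed. Infant death is dealt with separately in section 4.10.19, which ends the mother's participation, so it is not an example of this rule. All of that stands. It does not settle the matter. A woman too ill or too mobile to explain herself may be recorded as having no reason. And one who can be asked to leave has been reached, so her infant's status could be obtained at that contact.

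A second reply is that loss is already allowed for. Section 4.10.18 calls its rates a worst case and expects mobile phones to limit loss, Table 1 recovers some delivery samples, and nothing bars a late woman from her next scheduled visit. This also stands, and the protocol does not show that the rules push loss past that allowance. An allowance for numbers does not address who is lost, however, and none of these points softens the window condition itself.

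A third reply is cost: section 4.10.23 says current funds suffice for baseline surveys, and Table 6 shows staff allowances for six months only. That is a fair limit on open-ended tracing, though not on accepting a woman who attends late.

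**Conclusion.** The point holds as a design weakness worth correcting. As worded, section 4.8 forgoes obtainable data through the window and permits avoidable loss of mother and infant through the discontinuation rule. Its size can be shown only by example: up to 72 of 96 postnatal weeks for a woman discontinued after weeks 14 and 24, and a window covering 4% to 8% of the two 24-week gaps, the range reflecting its unstated direction. The total loss attributable to the rules cannot be computed from the protocol.

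Three stronger readings are tempting and are not supported.
- A reader might infer that the plan itself produces informative loss. The protocol has no data linking attendance to outcome, so only a risk can be claimed.
- A reader might apply the 8% figure to week 48 as well. The gap before that visit is 84 days, and 8% in the long gaps already assumes a two-sided window.
- A reader might add that the evaluable number already misses the stated minimum of 417 infants, since 600 × 0.85 × 0.80 = 408. Section 4.10.18 does not say which denominator 417 refers to, and on all 1200 the same calculation gives 816. This point does not rest on that comparison.

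**What to change.** Amend section 4.8 as follows.
- Keep seven days as a scheduling target and state its direction. Use it to label visits as in or out of window in the analysis, not as a condition for collecting data.
- See women who attend late, record the actual visit date and the reason for any missed visit, and use actual dates in the analysis.
- Replace study-initiated discontinuation for missed visits with continued follow-up of the pair until consent is withdrawn. Where visits are no longer attended and consent allows, obtain at least infant vital status and key outcomes by telephone. The separate provision on child death in section 4.10.19 is not affected.

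The cost is mainly protocol wording. Some visits will fall at irregular times, which the analysis must accommodate, and there will be modest extra contact effort. Table 6 already includes handsets, airtime and data for 24 months. Staff time beyond the funded period is the real constraint, and the intensity of tracing can be set accordingly.

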/Test	Required	Volume/gra	labour	7-10 Day	6 wks	10 wks	14 wks	24 wks	36 wks	48 wks	72 wks	96 wks
	(volume)	m		рр	рр	рр	рр	рр	рр	рр	рр	рр
CMV / HBV/ HCV	serum(1 mL)	✓ (1
HIV testing/all negatives	Plasma (1 mL)	1	~	1	1	1	1	1	~	1	1	1
STI serology												
Parasites At least 3 specimens	Stool(10 g) Anal swab	1	1	1	1	1	1	1	1	1	1	1
FBC/Differentials/pla telets	Plasma (5mL)	√			1		1			1		1
Markers of immune	Blood (10mL)	1		✓	✓	✓	1	1	1	1	1	√
activation, cytokines levels and trends	Cord blood (10mL)		~									
	Amniotic fluid (10mL)		1									
	Breast milk(10 mL)			1	1	1	1	1	1	1	1	1
Urine	urinalysis	1			1			1				1
Biochemistry	Plasma (5 mL)	✓			1		1			1		1
Panel	Sugar (3 mL)	√			✓		1			1		✓
Restriction factors	Cord blood		✓									
	Breast milk			1	✓	✓	✓	1	✓	1	✓	✓
				FOR	HIV POSI	TIVES ONL	Y					
T cell profile	PBMCs	✓						1	✓	 ✓ 	1	 ✓
HIV RNA load*	Whole blood	√ *										
HLA/KIR host genetics												
HIV genetic diversity for Transmission linkages**	Whole blood	~										V

Table 2: Type, Volume, intervals of collection and Purpose of Maternal Specimens Required

*Re-testing with be done for all Unsuppressed HIV load every 3 months ** for all acute HIV infections

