4.10.19 Ethics Statement

Ethical approval will be sought from the necessary institutional review boards, JREC and MRCZ. All study participants will give written informed consent. Permission for storage and future use of biological specimens, external shipping of specimens including genetic testing of blood samples will also be sought. This observational study involves minimal risks to both the mother and the baby hence one parental consent is sufficient. However, in case of death of the mother re-consenting will be done from either the father or any family member who shall have legal responsibility for the care and custody of the baby. In case of a child death, the mother will cease to continue participating in the study.

Permission has already been obtained from Harare City Health. The sensitivity of HIV infection and sexuality means that the mother's emotional response is a potential risk. Anxiety associated with sample testing and waiting for the results for HIV exposed children may also be experienced. Nevertheless the study will minimize such risks by providing the necessary education and counselling through the research nurses and where necessary, referring them to the appropriate clinics. Health education and counselling on pregnancy, delivery and childcare will be given to mothers on a continuous basis at every visit. The study will offer consultation and basic treatment to both the mother and child. Whenever necessary referrals will made through the clinic.

Each sub-study will apply for their respective ethical approvals to all the relevant ethical boards before they can access the data and/or specimens. However, some sub-studies may require separate consent forms should they entail collection of additional data from study participants. Those that rely on specimens and data collected through main study will need no additional informed consent.

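### Tables 1 and 2 disagree on when amniotic fluid is collected: Table 1 adds an antenatal collection and an impossible one at 6 weeks postpartum to the collection in labour

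*Protocol*

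**What the plan says.** Section 4.8 (Mothers' Procedures) lists the maternal specimens and points to Table 1 for amounts and purposes: "Biological specimens blood, cord blood, amniotic fluid, breast milk urine and stool will be collected at different visit with the respective quantities". The numeric columns of Table 1 run blood, stool, breast milk, urine, amniotic fluid, cord blood. The rows that matter are:

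- Visit 1, in pregnancy: "HIV+ 30 20 - 100 50" and "In Pregnancy HIV- 25 20 100 50".
- Visit 2, delivery, HIV-positive: "HIV+ 10 20 100 50 50". The HIV-negative row also ends in 50 and 50.
- Visit 4, 6 weeks postpartum, HIV-negative: "HIV- 10 20 10 100 50". The HIV-positive row stops at urine.

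Table 2, in the same section, has one amniotic fluid entry. It begins "Amniotic fluid (10mL", belongs to the immune activation and cytokine tests, and is ticked in the labour column only.

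Section 4.10.5 (Determination of Coinfections) also names amniotic fluid as a specimen to be tested, without tying it to a visit. Section 4.10.19 (Ethics Statement) says "This observational study involves minimal risks to both the mother and the baby" and concludes from this that consent from one parent is enough.

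**The concern.** The two tables are the working instructions for specimen collection, and they give different collection times for a specimen taken from pregnant women. Staff using Table 1 would expect amniotic fluid at enrolment, before labour. Staff using Table 2 would not.

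Three things are at stake:

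- **Compliance.** Monitors are to check compliance with the current protocol (section 4.10.20), and readiness to give the specimens the study needs is an inclusion criterion (section 4.4). Both require one answer on what is collected and when.
- **Risk statement.** Collection at 28-36 weeks would need a procedure that the protocol does not describe. That bears on the minimal-risk statement.
- **Data.** Amniotic fluid results could come from two different times, or appear missing at a visit where no collection was intended.

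**Working it through.** No sample-size or power figure is involved. The check sets the tables side by side.

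**1. Do the values sit under the right columns in Table 1?**

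| Visit | Group | Blood | Stool | Breast milk | Urine | Amniotic fluid | Cord blood |
|---|---|---|---|---|---|---|---|
| 1, in pregnancy | HIV+ | 30 | 20 | - | 100 | 50 | blank |
| 1, in pregnancy | HIV- | 25 | 20 | blank | 100 | 50 | blank |
| 2, delivery | HIV+ | 10 | 20 | blank | 100 | 50 | 50 |
| 2, delivery | HIV- | 5 | 20 | blank | 100 | 50 | 50 |
| 4, 6 weeks | HIV+ | 20 | 20 | 10 | 100 | blank | blank |
| 4, 6 weeks | HIV- | 10 | 20 | 10 | 100 | 50 | blank |

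Urine is 100 in every row. The dash or blank for breast milk before delivery is kept. The HIV-negative rows for visits 5 to 11 read 10, 20, 10, 100, so the visit 4 HIV-negative row is that same row with an extra 50. If that 50 belonged under cord blood it would be equally impossible 6 weeks after delivery.

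**2. Compare timing with Table 2.**

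| Visit | Table 1, HIV+ | Table 1, HIV- | Table 2 |
|---|---|---|---|
| 1, in pregnancy | yes | yes | no |
| 2, delivery or labour | yes | yes | yes |
| 4, 6 weeks postpartum | no | yes | no |

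Table 1 has 2 + 2 + 1 = 5 amniotic fluid entries. Two agree with Table 2 on timing, and 5 - 2 = 3 do not. Visit 1 is enrolment at 28-36 weeks and is listed separately from delivery, so the visit 1 entries are not the labour collection under another name.

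**3. Does other text settle it?** Section 4.10.5 schedules maternal coinfection screening at enrolment and at 24 months, then lists peripheral blood, cord blood and amniotic fluid as test material. Cord blood cannot come from either of those visits, so the list cannot be read as an enrolment list. Nor does it confine amniotic fluid to labour. The coinfection row of Table 2 names serum only.

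**4. Is there a volume conflict?** Table 1 gives the total volume per visit and Table 2 the volume per test. Of the 50 mL total at delivery, Table 2 itemises 10 mL, leaving 50 - 10 = 40 mL not itemised. Section 4.10.5 and the Table 1 footnote name coinfection testing as a further use, so a total above one assay's volume is not a contradiction.

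**5. Does it touch the ethics statement?** The text shown describes no method for obtaining amniotic fluid before labour. With collection in labour only, the minimal-risk statement raises no question on this point. With collection at 28-36 weeks, it would need to be justified.

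**The case against.** The strongest reply is that these are clerical slips in one column. Table 2 ticks labour only, no antenatal procedure is described anywhere, and the minimal-risk statement fits Table 2. The 6-week entry cannot be carried out, so it harms no participant and enters no analysis. The tables are also visibly damaged in the PDF text, and a shifted cell cannot be excluded.

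Much of this stands. A slip is a plausible explanation, and the original layout should be checked first. But a shift would have to affect three rows while leaving every other value in them in place. A slip in an operative schedule still has to be corrected, and the protocol does not say which table governs.

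A reader might infer three stronger points that the document does not support:

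- **A fivefold volume contradiction (50 against 10 mL).** The two tables measure different things, total per visit and volume per test. At most, Table 2 does not itemise the total in Table 1.
- **A cord blood discrepancy.** Both tables place cord blood at delivery. Table 2 has a second cord blood row, for restriction factors, with no volume, so it does not fix cord blood at 10 mL.
- **An established breach of safety or consent.** This follows only if the antenatal entry is meant literally. The consent pages are not available, so nothing can be said about what women are told.

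**Conclusion.** The timing conflict is real. Three of five amniotic fluid entries in Table 1 have no match in Table 2: visit 1 for both HIV groups, and 6 weeks postpartum for HIV-negative women. The last is impossible whichever table governs. By planned enrolment the entries cover 1200 women at visit 1 and 600 at 6 weeks. These figures show the scope of the instruction; they are not counts of women exposed to a procedure.

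The tension with the minimal-risk and one-parent consent statement is conditional on the antenatal entry being intended. The whole reading assumes that the columns in the PDF text match the original page, which the surrounding values make likely but do not prove. Which collection time is intended is for the sponsor and investigators to state.

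**What to change.** First check the Table 1 cells against the original page layout. Then:

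- Reconcile Table 1, Table 2 and section 4.10.5 so that all three state the same visits and the same groups for amniotic fluid.
- Remove the 6-week postpartum entry, since the specimen cannot exist then.
- Confirm that the reconciled schedule agrees with the minimal-risk statement in section 4.10.19 and with the consent material.
- Optionally, itemise the Table 1 total by use, so that the per-test volumes in Table 2 can be traced to it.

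The cost is a correction to a few table cells and a read-through of two sections. If an antenatal collection is intended, the cost is larger: the protocol would have to describe it and the risk statement would have to be reviewed.

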	different comorbidities in isolation or combinations among mothers and infants.
	uniterent comorbiances in isolation of comornations among motiers and infants.
	-
	4. To correlate maternal plasma viral load, soluble biomarkers immune activation profiles and diseases
	4. To correlate maternal plasma viral load, soluble biomarkers immune activation profiles and diseases progression and duration of HAART treatment among HIV+ mothers
	 To correlate maternal plasma viral load, soluble biomarkers immune activation profiles and diseases progression and duration of HAART treatment among HIV+ mothers To determine any association of different HAART regimens and pregnancy outcome, infant growth and
Primary	 To correlate maternal plasma viral load, soluble biomarkers immune activation profiles and diseases progression and duration of HAART treatment among HIV+ mothers To determine any association of different HAART regimens and pregnancy outcome, infant growth and immune/neuro-development among HIV+ mothers
Primary end points	 To correlate maternal plasma viral load, soluble biomarkers immune activation profiles and diseases progression and duration of HAART treatment among HIV+ mothers To determine any association of different HAART regimens and pregnancy outcome, infant growth and immune/neuro-development among HIV+ mothers Prevalence, trends and incidence of comorbidities among HIV+ and HIV- mothers
•	 To correlate maternal plasma viral load, soluble biomarkers immune activation profiles and diseases progression and duration of HAART treatment among HIV+ mothers To determine any association of different HAART regimens and pregnancy outcome, infant growth and immune/neuro-development among HIV+ mothers Prevalence, trends and incidence of comorbidities among HIV+ and HIV- mothers Pregnancy outcomes for HIV-/+ mothers with different comorbidities with or without different HAART
•	 To correlate maternal plasma viral load, soluble biomarkers immune activation profiles and diseases progression and duration of HAART treatment among HIV+ mothers To determine any association of different HAART regimens and pregnancy outcome, infant growth and immune/neuro-development among HIV+ mothers Prevalence, trends and incidence of comorbidities among HIV+ and HIV- mothers Pregnancy outcomes for HIV-/+ mothers with different comorbidities with or without different HAART regimens

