4.10.5 Determination of Coinfections

HBs Ag/anti-HB/anti-HCV/anti-CMV will be screened at enrolment and at 24 month postpartum for the mothers using qualitative rapid immunochromatographic assays. These will coinfections will be tested in the peripheral blood, cord blood including amniotic fluid. Stool specimen will be examined for intestinal parasitic infections at the age of 7-10 days and six weeks old for the infants.

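### Tables 1 and 2 give incompatible maternal blood volumes: from 6 weeks the volume stated for HIV-negative women cannot carry the scheduled panel

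*Protocol*

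**What the plan says.** Table 1 in section 4.8, "Types and total Volumes of Maternal Specimen Required", is headed "Total Volume of Specimen Required". Its blood column gives these volumes:

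- HIV-negative women: 25 mL in pregnancy, 5 mL at delivery, none at 7-10 days, 10 mL at every visit from 6 to 96 weeks.
- HIV-positive women: 30 mL, 10 mL, none, then 20 mL at every visit.

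Table 2, "Type, Volume, intervals of collection and Purpose of Maternal Specimens Required", lists the tests. Above the subheading that limits the remaining rows to HIV-positive women, the maternal blood items are:

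- CMV/HBV/HCV, 1 mL. Section 4.10.5 gives the timing: these "will be screened at enrolment and at 24 month postpartum for the mothers".
- "HIV testing/all negatives", 1 mL at every visit.
- Full blood count, 5 mL at enrolment, 6, 14, 48 and 96 weeks.
- Immune activation markers and cytokines, 10 mL at enrolment and at every visit from 7-10 days on.
- Biochemistry, 5 mL, and sugar, 3 mL, both at the same visits as the blood count.

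Below that subheading, "T cell profile" (on PBMCs) is ticked at enrolment and at 24, 36, 48, 72 and 96 weeks with no volume. Viral load and the genetic assays also have none.

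Section 4.10.1 places the blood count and chemistry at baseline, 6 weeks and then six-monthly. That schedule has no 14-week test.

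The Protocol Summary lists among the primary end points "Prevalence, trends and incidence of comorbidities among HIV+ and HIV- mothers".

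**The concern.** A table of total volumes and a table of per-test volumes should agree visit by visit, or at least the total should never be the smaller. Here it is smaller at most postpartum visits. In HIV-negative women the immune-marker sample alone takes the whole 10 mL, leaving nothing for the blood count, chemistry, glucose or HIV test.

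Those tests supply follow-up data on anaemia and diabetes, which hypothesis 1 in section 2.1 compares by HIV status. The gap is larger in HIV-negative women, so sites improvising within the Table 1 volume could lose more of these results in the comparison group. The document gives no rule for a short draw.

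**Working it through.** **Inputs.** Per-test volumes and visits come from Table 2, with CMV/HBV/HCV timing from section 4.10.5. Totals come from Table 1.

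**Formula.** Need at a visit = sum of the Table 2 maternal blood, serum and plasma volumes ticked there. The 1 mL HIV test counts only for HIV-negative women. For HIV-positive women only tests with a stated volume are counted.

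**The plan's own figure first.** HIV-negative, enrolment: 1 (CMV/HBV/HCV) + 1 (HIV) + 5 (blood count) + 10 (immune markers) + 5 (biochemistry) + 3 (sugar) = 25 mL. Table 1 also says 25 mL.

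**The same sum at the main postpartum visits.**

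- HIV-negative, 6, 14 and 48 weeks: 1 + 5 + 10 + 5 + 3 = 24 mL. At 96 weeks: 24 + 1 = 25 mL.
- HIV-positive, 6, 14 and 48 weeks: 5 + 10 + 5 + 3 = 23 mL. At 96 weeks: 23 + 1 = 24 mL.

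| Visit | HIV− need | HIV− Table 1 | Difference | HIV+ need | HIV+ Table 1 | Difference |
|---|---|---|---|---|---|---|
| Enrolment | 25 | 25 | 0 | 24* | 30 | +6* |
| Delivery | 1 | 5 | +4 | 0 | 10 | +10 |
| 7-10 days | 11 | none | −11 | 10 | none | −10 |
| 6 weeks | 24 | 10 | −14 | 23 | 20 | −3 |
| 10 weeks | 11 | 10 | −1 | 10 | 20 | +10 |
| 14 weeks | 24 | 10 | −14 | 23 | 20 | −3 |
| 24, 36, 72 weeks | 11 | 10 | −1 | 10* | 20 | +10* |
| 48 weeks | 24 | 10 | −14 | 23* | 20 | −3* |
| 96 weeks | 25 | 10 | −15 | 24* | 20 | −4* |

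Volumes in mL. *Before HIV-specific samples with no stated volume, so the true difference is less favourable.

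**Size relative to need.** HIV-negative: 14/24 = 58% and 15/25 = 60%. HIV-positive: 3/23 = 13% and 4/24 = 17%, before PBMCs at 48 and 96 weeks.

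**Does tube sharing close the gap?** Suppose every other test is run from the 10 mL immune-marker sample. Section 4.10.3.1 still requires a separate grey-topped tube for glucose and HbA1c, for which Table 2 lists 3 mL. Then 10 + 3 = 13 mL, more than the 10 mL for HIV-negative women and less than the 20 mL for HIV-positive women.

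**Does the section 4.10.1 timetable close it?** If the six-monthly tests fall at 24, 48, 72 and 96 weeks, the 5 + 5 + 3 = 13 mL panel leaves 14 weeks and is added at 24 and 72 weeks. HIV-negative need becomes 11 mL at 14 weeks and 11 + 13 = 24 mL at 24 and 72 weeks. The 14 mL gap moves to those two visits, and 6, 48 and 96 weeks stay as above.

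**The case against.** The strongest reply is that Table 1 may never have been built as the sum of Table 2. The exact match occurs only for HIV-negative women at enrolment. At delivery Table 1 exceeds the listed blood items, and other specimens do not sum either: 20 g of stool against 10 g, and 50 mL of cord blood against 10 mL. Table 1's footnote links blood mainly to immune profiles and coinfections, and 10 mL equals the immune-marker draw. This stands as a caution about intent. It does not resolve the conflict: a total above the listed items can be an allowance, but one below them cannot be carried out as written.

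Second, the laboratory may need far less than Table 2 lists. Section 4.10.7.5 measures seven cytokines in 50 µL, section 1.11 foresees several markers from one plasma sample, and Table 2 labels the blood count as plasma although section 4.10.2 uses EDTA blood. This also stands, and it is a reason to consider correcting Table 2 rather than Table 1. With the stated volumes, sharing still leaves 13 mL against 10 mL. If the plasma and serum volumes are literal, the whole-blood need is larger; no conversion is given.

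Third, a reader might infer that sites must drop particular tests, that follow-up incidence will be lowest in HIV-negative women, and that the comparison is therefore biased. The document does not support this. It does not say what would be dropped, and the HIV test, a rapid assay under section 4.10.8, is an unlikely casualty. Results lost only because of a fixed draw volume are lost regardless of a woman's outcome within her group. That costs precision and follow-up data; it does not by itself lower incidence.

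Fourth, a reader might infer that HIV-positive women have blood to spare at 10, 24, 36 and 72 weeks. At three of these four visits a PBMC sample of unknown volume is also due. Totals across visits would mislead too, since volume unused at one visit cannot supply another.

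**Conclusion.** The contradiction is real and rests on the protocol's own figures. HIV-negative women are short by 14 mL at 6, 14 and 48 weeks and by 15 mL at 96 weeks. HIV-positive women are short by at least 3 mL and 4 mL at the same visits. The 7-10 day visit has a 10 mL sample scheduled and no blood allotted in either group, and the 14-week panel conflicts with section 4.10.1.

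The figures assume that Table 2 volumes add, as they do at enrolment, and that its ticks are read correctly; some marks, including the CMV row, are unclear in the text available, though section 4.10.5 supports the timing used for that row.

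The consequence is a risk, not a certainty, of uneven loss of follow-up blood count, chemistry and glucose data by HIV status. That is enough to require reconciliation, because these data serve a primary end point. It does not show that the HIV-positive versus HIV-negative comparison is biased.

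**What to change.** Reconcile Table 1, Table 2 and section 4.10.1. Which volume or timetable is right is for the investigators to decide.

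- Make each Table 1 blood total cover the Table 2 items at that visit, including delivery and 7-10 days, by revising Table 1 or the per-test volumes in Table 2.
- Settle one timetable for the blood count and chemistry across Table 2 and section 4.10.1.
- Allow the same volume for the shared panel in both groups. State volumes for the HIV-specific assays and add them on top.
- Apply any rule for short draws identically in both groups. It should not rank biomarkers as exploratory: they are primary objective 3 in the Protocol Summary and the subject of hypothesis 2 in section 2.1.

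The cost is a protocol edit. Raising drawn volumes would also need ethics notification; cutting per-test volumes would leave less stored sample.
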